APPENDIX 4 IMMUNE ADVERSE EVENT MANAGEMENT ALGORITHMS

GI Adverse Event Management Algorithm

[figure not shown]
Rule out non-inflammatory causes. If non-inflammatory cause is identified, treat accordingly and continue I-O therapy. Opiates/narcotics may mask symptoms of perforation. Infliximab should not be used in cases of perforation or sepsis.

Patients on IV steroids may be switched to an equivalent dose of oral corticosteroids (e.g. prednisone) at start of tapering or earlier, once sustained clinical improvement is observed. Lower bioavailability of oral corticosteroids should be taken into account when switching to the equivalent dose of oral corticosteroids

Renal Adverse Event Management Algorithm

[figure not shown]
Rule out non-inflammatory causes. If non-inflammatory cause, treat accordingly and continue I-O therapy

Patients on IV steroids may be switched to an equivalent dose of oral corticosteroids (e.g. prednisone) at start of tapering or earlier, once sustained clinical improvement is observed. Lower bioavailability of oral corticosteroids should be taken into account when switching to the equivalent dose of oral corticosteroids

Pulmonary Adverse Event Management Algorithm

[figure not shown]
Rule out non-inflammatory causes. If non-inflammatory cause, treat accordingly and continue I-O therapy. Evaluate with imaging and pulmonary consultation.

Patients on IV steroids may be switched to an equivalent dose of oral corticosteroids (e.g. prednisone) at start of tapering or earlier, once sustained clinical improvement is observed. Lower bioavailability of oral corticosteroids should be taken into account when switching to the equivalent dose of oral corticosteroids.

Hepatic Adverse Event Management Algorithm

Rule out non-inflammatory causes. If non-inflammatory cause, treat accordingly and continue I-O therapy. Consider imaging for obstruction.

[figure not shown]
Patients on IV steroids may be switched to an equivalent dose of oral corticosteroids (e.g. prednisone) at start of tapering or earlier, once sustained clinical improvement is observed. Lower bioavailability of oral corticosteroids should be taken into account when switching to the equivalent dose of oral corticosteroids.

*I-O therapy may be delayed rather than discontinued if AST/ALT ≤ 8 x ULN and T.bili ≤ 5 x ULN.

**The recommended starting dose for grade 4 hepatitis is 2 mg/kg/day methylprednisolone IV.

Endocrinopathy Management Algorithm

[figure not shown]
Rule out non-inflammatory causes. If non-inflammatory cause, treat accordingly and continue I-O therapy. Consider visual field testing, endocrinology consultation, and imaging.

Patients on IV steroids may be switched to an equivalent dose of oral corticosteroids (e.g. prednisone) at start of tapering or earlier, once sustained clinical improvement is observed. Lower bioavailability of oral corticosteroids should be taken into account when switching to the equivalent dose of oral corticosteroids.

Skin Adverse Event Management Algorithm

Rule out non-inflammatory causes. If non-inflammatory cause, treat accordingly and continue I-O therapy.

[figure not shown]

Patients on IV steroids may be switched to an equivalent dose of oral corticosteroids (e.g. prednisone) at start of tapering or earlier, once sustained clinical improvement is observed. Lower bioavailability of oral corticosteroids should be taken into account when switching to the equivalent dose of oral corticosteroids.

*Refer to NCI CTCAE v4 for term-specific grading criteria.

Neurological Adverse Event Management Algorithm

Rule out non-inflammatory causes. If non-inflammatory cause, treat accordingly and continue I-O therapy.

Patients on IV steroids may be switched to an equivalent dose of oral corticosteroids (e.g. prednisone) at start of tapering or earlier, once sustained clinical improvement is observed. Lower bioavailability of oral corticosteroids should be taken into account when switching to the equivalent dose of oral corticosteroids.

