4.3 Discontinuation of Subjects following any Treatment with Study Drug

Subjects MUST discontinue investigational product (and non-investigational product at the discretion of the investigator) for any of the following reasons:

- Subject's request to stop study treatment
- Progression of the target lesion
- Any clinical adverse event (AE), laboratory abnormality or intercurrent illness which, in the opinion of the investigator, indicates that continued participation in the study is not in the best interest of the subject
- Termination of the study by Bristol-Myers Squibb (BMS)
- Loss of ability to freely provide consent through imprisonment or involuntarily incarceration for treatment of either a psychiatric or physical (eg, infectious disease) illness
- Additional protocol specified reasons for discontinuation (see Section 4.5.7).

In the case of pregnancy, the study drug will be permanently discontinued in an appropriate manner unless the investigator determines a possible favorable benefit/risk ratio that warrants continuation of study drug.

All subjects who discontinue study drug should comply with protocol specified follow-up procedures as outlined in [Section 7](#). The only exception to this requirement is when a subject withdraws consent for all study procedures including post-treatment study follow-up or loses the ability to consent freely (ie, is imprisoned or involuntarily incarcerated for the treatment of either a psychiatric or physical illness).

If study drug is discontinued prior to the subject's completion of the study, the reason for the discontinuation must be documented in the subject's medical records and entered on the appropriate case report form (CRF) page.

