5.5.6 Criteria to Resume Treatment

Subjects may resume treatment with study drug when the drug-related AE(s) resolve to Grade ≤ 1 or baseline value, with the following exceptions:

- Subjects may resume treatment in the presence of Grade 2 fatigue
- Subjects who have not experienced a Grade 3 drug-related skin AE may resume treatment in the presence of Grade 2 skin toxicity
- Subjects with baseline Grade 1 AST/ALT or total bilirubin who require dose delays for reasons other than a 2-grade shift in AST/ALT or total bilirubin may resume treatment in the presence of Grade 2 AST/ALT OR total bilirubin
- Subjects with combined Grade 2 AST/ALT AND total bilirubin values meeting discontinuation parameters (Section XX) should have treatment permanently discontinued
- Drug-related pulmonary toxicity, diarrhea, or colitis, must have resolved to baseline before treatment is resumed
- Drug-related endocrinopathies adequately controlled with only physiologic hormone replacement may resume treatment

If the criteria to resume treatment are met, the subject should restart treatment at the next scheduled timepoint per protocol. However, if the treatment is delayed past the next scheduled timepoint per protocol, the next scheduled timepoint will be delayed until dosing resumes. If the design of the study defines that doses may not be omitted [skipped], strongly recommend adding “Doses may not be skipped”

If treatment is delayed > 6 weeks, the subject must be permanently discontinued from study therapy, except as specified in discontinuation section.

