5.5.7 Discontinuation Criteria

Treatment should be permanently discontinued for the following:

- Any Grade 2 drug-related uveitis or eye pain or blurred vision that does not respond to topical therapy and does not improve to Grade 1 severity within the re-treatment period OR requires systemic treatment
- Any Grade 3 non-skin, drug-related adverse event lasting > 7 days, with the following exceptions for drug-related laboratory abnormalities, uveitis, pneumonitis, bronchospasm, diarrhea, colitis, neurologic adverse event, hypersensitivity reactions, and infusion reactions
 - Grade 3 drug-related uveitis, pneumonitis, bronchospasm, diarrhea, colitis, neurologic adverse event, hypersensitivity reaction, or infusion reaction of any duration requires discontinuation
 - Grade 3 drug-related laboratory abnormalities do not require treatment discontinuation except those noted below
 - Grade 3 drug-related thrombocytopenia > 7 days or associated with bleeding requires discontinuation
 - Any drug-related liver function test (LFT) abnormality that meets the following criteria require discontinuation:
 - AST or ALT > 8 x ULN
 - Total bilirubin > 5 x ULN
 - Concurrent AST or ALT > 3 x ULN and total bilirubin > 2 x ULN
- Any Grade 4 drug-related adverse event or laboratory abnormality, except for the following events which do not require discontinuation:
 - Isolated Grade 4 amylase or lipase abnormalities that are not associated with symptoms or clinical manifestations of pancreatitis and decrease to < Grade 4 within 1 week of onset.
 - Isolated Grade 4 electrolyte imbalances/abnormalities that are not associated with clinical sequelae and are corrected with supplementation/appropriate management within 72 hours of their onset
- Any dosing interruption lasting > 6 weeks with the following exceptions:

- Dosing interruptions to allow for prolonged steroid tapers to manage drug-related adverse events are allowed. Prior to re-initiating treatment in a subject with a dosing interruption lasting > 6 weeks, the Investigator must be consulted. Tumor assessments should continue as per protocol even if dosing is interrupted
- Dosing interruptions > 6 weeks that occur for non-drug-related reasons may be allowed if approved by the Investigator. Prior to re-initiating treatment in a subject with a dosing interruption lasting > 6 weeks, the Investigator must be consulted. Tumor assessments should continue as per protocol even if dosing is interrupted

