8.6 Potential Drug Induced Liver Injury (DILI)

Wherever possible, timely confirmation of initial liver-related laboratory abnormalities should occur prior to the reporting of a potential DILI event. All occurrences of potential DILIs, meeting the defined criteria, must be reported as SAEs.

Potential drug induced liver injury is defined as:

AT (ALT or AST) elevation > 3 times ULN (5 x ULN in patients with liver metastasis) AND

Total bilirubin > 2 times ULN, without initial findings of cholestasis (elevated serum alkaline phosphatase),

AND

No other immediately apparent possible causes of AT elevation and hyperbilirubinemia, including, but not limited to, viral hepatitis, pre-existing chronic or acute liver disease, or the administration of other drug(s) known to be hepatotoxic.

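### As worded, the Appendix 4 hepatic footnote permits delay for some combined AST/ALT and bilirubin elevations at which Section 5.5.7 requires discontinuation: a minor safety-text inconsistency

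*Combined protocol and SAP*

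**What the plan says.** Section 5.5.7 (Discontinuation Criteria) introduces the liver limits with "Any drug-related liver function test (LFT) abnormality that meets the following criteria require discontinuation". Three limits follow, and any one is enough: AST or ALT above 8 x ULN; total bilirubin above 5 x ULN; or "Concurrent AST or ALT > 3 x ULN and total bilirubin > 2 x ULN".

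The hepatic algorithm in Appendix 4 carries this footnote: "I-O therapy may be delayed rather than discontinued if AST/ALT ≤ 8 x ULN and T.bili ≤ 5 x ULN". The flow chart to which it belongs is not shown.

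Section 5.5.6 (Criteria to Resume Treatment) opens with "Subjects may resume treatment with study drug when the drug-related AE(s) resolve to Grade" 1 or lower, or to the baseline value, subject to listed exceptions. One exception reads: "Subjects with combined Grade 2 AST/ALT AND total bilirubin values meeting discontinuation parameters (Section XX) should have treatment permanently discontinued".

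Section 4.3 says that subjects must discontinue for several reasons, the last being "Additional protocol specified reasons for discontinuation (see Section 4.5.7"). Section 5.5.4 introduces the algorithms as help for investigators, recommends their use, and attaches them for reference. It does not say which text governs if an algorithm and Section 5.5.7 differ.

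**The concern.** The third limit in Section 5.5.7 catches a patient whose transaminases and bilirubin rise together, even when neither value alone reaches its own stop limit. The footnote tests each value only against its own limit. A clinician working from the Appendix 4 page could therefore read it as permission to hold treatment in a patient for whom Section 5.5.7 ends it.

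Delay would not look out of place. Section 5.5.5 also calls for dose delay for drug-related AST, ALT or bilirubin toxicity, and Section 5.5.4 recommends intervention according to the algorithms. What is at stake is a patient-safety stop rule. No endpoint or error rate is involved.

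**Working it through.** The plan states no figure to reproduce. The check compares the two rules as logical conditions.

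**Inputs.** Let A be the higher of AST and ALT and B the total bilirubin, both in multiples of ULN, in a drug-related case.

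- Section 5.5.7, stop required: A > 8, or B > 5, or (A > 3 and B > 2).
- Appendix 4 footnote, delay permitted: A ≤ 8 and B ≤ 5.

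**Overlap.** Where the footnote applies, A > 8 and B > 5 are both ruled out, so only the third stop limit can still be met. Both rules therefore apply exactly where 3 < A ≤ 8 and 2 < B ≤ 5.

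**Grid check.** In steps of 0.1 x ULN (A from 0 to 12, B from 0 to 8), the rules disagree at 1,500 points. These run from A = 3.1 to 8.0 (50 values) and B = 2.1 to 5.0 (30 values), and 50 × 30 = 1,500. The conflict fills that rectangle and occurs nowhere else.

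| AST/ALT (x ULN) | Bilirubin (x ULN) | Footnote permits delay | 5.5.7 requires stop |
|---|---|---|---|
| 6 | 4 | yes | yes (conflict) |
| 4 | 2.5 | yes | yes (conflict) |
| 8 | 5 | yes | yes (conflict) |
| 6 | 1.5 | yes | no |
| 2 | 4 | yes | no |
| 3 | 2 | yes | no |
| 8.1 | 1 | no | yes |

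The single-value limits of 8 x and 5 x ULN agree exactly between the two texts. The whole conflict comes from the missing concurrent limit.

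**After the fix.** If the footnote also excludes (A > 3 and B > 2), each of the three stop conditions contradicts a condition for delay, and the overlap is empty.

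**Which text expresses the intent.** Section 5.5.7 lists the concurrent limit in plain terms, Section 5.5.6 repeats that combined elevations end treatment, and Section 4.3 makes protocol-specified discontinuation obligatory. The footnote is the outlier.

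**The case against.** The strongest reply is that the footnote is only part of the algorithm. Its asterisk belongs to a box in a chart that is not shown. That box may be limited to one grade, or the chart may treat concurrent elevation separately. This stands: the rectangle above is the largest zone of conflict the wording allows, and the true zone may be smaller.

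Second, the two texts differ in force. One requires and the other permits, and the algorithms are aids, so a site that stops complies with both. This also stands, and it is the main reason the point is minor. It does not make the permission correct.

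A reader might draw three stronger conclusions that the documents do not support.

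- *That a delayed patient could simply restart once tests recover.* The general resume sentence in Section 5.5.6 is subject to the exception that permanently stops combined Grade 2 elevations meeting the discontinuation limits. That exception names Grade 2 only, and the protocol does not give the grade cut-offs, so how much of the zone it covers cannot be read from the text. It nevertheless blocks the route for the values it names.
- *That the faulty pointers hide the stop rule.* Section 4.3 cites a Section 4.5.7 although Section 4 ends at 4.4.2, and Section 5.5.6 has an unfilled reference. But Section 5.5.7 directly follows 5.5.6, has a plain title and is listed in the table of contents. These are clerical errors and do not conceal the rule.
- *That the liver-injury definition in Section 8.6 widens the gap.* Its transaminase condition is "AT (ALT or AST) elevation > 3 times ULN (5 x ULN in patients with liver metastasis) AND" a bilirubin condition, and its consequence is that "All occurrences of potential DILIs, meeting the defined criteria, must be reported as SAEs". It is a reporting definition. The higher threshold with liver metastasis, and the wrong reference to that definition in Section 8.1, do not bear on when treatment must stop.

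**Conclusion.** The inconsistency is real on the wording and minor in weight. The footnote permits delay at AST/ALT above 3 and up to 8 x ULN with bilirubin above 2 and up to 5 x ULN, where Section 5.5.7 requires discontinuation of drug-related cases. The conflict may cover only part of that zone.

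This rests on two readings: that the footnote applies as written, which the missing chart leaves unverified, and that the case is drug-related, as Section 5.5.7 requires. The documents give no rate of concurrent elevation, so the number of patients affected cannot be estimated. The mandatory text already gives the safe answer, and a careful site would follow it. Design, sample size, error rates and analysis are untouched.

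**What to change.** First check the complete Appendix 4 chart to see which box carries the asterisk. Then:

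1. Add an exclusion to the footnote: *and not concurrent AST or ALT > 3 x ULN with total bilirubin > 2 x ULN (discontinue per Section 5.5.7)*.
2. State in Section 5.5.4 that Section 5.5.7 governs wherever an algorithm differs from it.
3. While editing, make both the unfilled reference in Section 5.5.6 and the reference to 4.5.7 in Section 4.3 point to Section 5.5.7.

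The cost is four short wording edits. The one drawback is that the footnote may then differ from the nivolumab brochure algorithm, which Section 5.5.4 recommends following and which is not available here for comparison. The precedence sentence in item 2 covers that.

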APPENDIX 5 EORTC QLQ-C30 (VER 3) FORM

We are interested in some things about you and your health. Please answer all of the questions yourself by circling the number that best applies to you. There are no "right" or "wrong" answers. The information that you provide will remain strictly confidential.

Please fill in your initials:
□□□□

Your birthdate (Day, Month, Year):
□□□□□□□□

Today's date (Day, Month, Year): 31
□□□□□□□□

	Not at All	A Little	Quite a Bit	Very Much
1. Do you have any trouble doing strenuous activities, like carrying a heavy shopping bag or a suitcase?	1	2	3	4
2. Do you have any trouble taking a long walk?	1	2	3	4
3. Do you have any trouble taking a short walk outside of the house?	1	2	3	4
4. Do you need to stay in bed or a chair during the day?	1	2	3	4
5. Do you need help with eating, dressing, washing yourself or using the toilet?	1	2	3	4

During the past week:	Not at All	A Little	Quite a Bit	Very Much
6. Were you limited in doing either your work or other daily activities?	1	2	3	4
7. Were you limited in pursuing your hobbies or other leisure time activities?	1	2	3	4
8. Were you short of breath?	1	2	3	4
9. Have you had pain?	1	2	3	4
10. Did you need to rest?	1	2	3	4
11. Have you had trouble sleeping?	1	2	3	4
12. Have you felt weak?	1	2	3	4
13. Have you lacked appetite?	1	2	3	4
14. Have you felt nauseated?	1	2	3	4
15. Have you vomited?	1	2	3	4

16. Have you been constipated? 1 2 3 4

During the past week:

	Not at All	A Little	Quite a Bit	Very Much
17. Have you had diarrhea?	1	2	3	4
18. Were you tired?	1	2	3	4
19. Did pain interfere with your daily activities?	1	2	3	4
20. Have you had difficulty in concentrating on things, like reading a newspaper or watching television?	1	2	3	4
21. Did you feel tense?	1	2	3	4
22. Did you worry?	1	2	3	4
23. Did you feel irritable?	1	2	3	4
24. Did you feel depressed?	1	2	3	4
25. Have you had difficulty remembering things?	1	2	3	4
26. Has your physical condition or medical treatment interfered with your family life?	1	2	3	4
27. Has your physical condition or medical treatment interfered with your social activities?	1	2	3	4
28. Has your physical condition or medical treatment caused you financial difficulties?	1	2	3	4

For the following questions please circle the number between 1 and 7 that best applies to you

29. How would you rate your overall health during the past week?

1 2 3 4 5 6 7

Very poor

Excellent

30. How would you rate your overall quality of life during the past week?

1 2 3 4 5 6 7

Very poor

Excellent
